included 312 patients who met the following criteria: (1) Had already received systemic steroid treatment for chronic GVHD at a prednisone-equivalent dose of at least 0.5 mg/kg/day, (2) also on an additional systemic immunosuppressive treatment when second-line treatment was started, and (3) received second-line treatment because of progressive GVHD manifestations after at least 1 week of initial treatment or because of lack of improvement after at least 2 weeks of initial treatment. Commonly used second-line treatments included mycophenolate mofetil, tacrolimus, sirolimus, extracorporeal photopheresis, cyclosporine, methotrexate, or other agents. By 6 months of second-line therapy, 44% had experienced treatment failure (composite of requirement of additional systemic immune suppression beyond second-line therapy, death, and malignancy relapse),¹⁸ and thus 6 month failure-free survival (FFS) was 56%. In multivariate analysis, three factors were significant determinants of treatment failure: high-risk disease at transplantation (defined as diseases other than low risk; low-risk disease categories included chronic myeloid leukemia in chronic phase, acute leukemia in first complete remission, myelodysplastic syndrome without excess blasts, and non-malignant diseases), lower gastrointestinal involvement as second-line treatment was added, and severe NIH global score as second-line treatment was added. These three factors were used to define risk groups: low-risk had no risk factors, intermediate-risk included those with 1 risk factor, and high-risk included those with 2-3 risk factors. The cumulative incidence of 6 month treatment failure was 33% for low-risk, 41% for intermediate risk, and 56% for high risk.

Immune modulation following proteasome inhibition

Proteasome inhibition exerts powerful effects on immune cells implicated in GVHD pathogenesis. Pre-clinical and clinical data provide robust support for this concept.^{19,20} Proteasome inhibitors interfere with antigen processing and presentation, as well as signaling cascades involved in immune cell function and survival. In dendritic cells (DC), there is impaired maturation, co-stimulatory molecule expression, and reduction of pro-inflammatory cytokines. T lymphocytes demonstrate apoptosis, reduced proliferation, impaired pro-inflammatory cytokine production, as well as expansion of regulatory T cells (Treg). B cell proliferation is decreased, and reduced antibody production is observed

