2. STUDY OBJECTIVES

2.1 Primary Objectives

Determine the proportion of subjects with treatment failure by 6 months of Ixazomib treatment for chronic GVHD.

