4.2 Number of Patients

A total of 50 patients will be enrolled. A patient is considered enrolled the day the informed consent form is signed. In order to control the speed of enrollment and ensure that no more than 50 subjects are enrolled across the study, each participant must be approved by the coordinating center at Fred Hutchinson prior to enrollment.

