5. STUDY POPULATION

5.1 Inclusion Criteria

Each patient must meet all of the following inclusion criteria to be enrolled in the study:

1. Age 18 years or older.
2. Voluntary written consent must be given before performance of any study related procedure not part of standard medical care, with the understanding that consent may be withdrawn by the patient at any time without prejudice to future medical care.
3. Female patients who:
 - Are postmenopausal for at least 1 year before the screening visit, OR
 - Are surgically sterile, OR
 - If they are of childbearing potential, agree to practice 2 effective methods of contraception, at the same time, from the time of signing the informed consent form through 90 days after the last dose of study drug, OR
 - Agree to practice true abstinence or exclusively non-heterosexual activity when this is in line with the preferred and usual lifestyle of the subject. (Periodic abstinence [eg, calendar, ovulation, symptothermal, post-ovulation methods] and withdrawal are not acceptable methods of contraception.)

Male patients, even if surgically sterilized (ie, status post-vasectomy), must agree to one of the following:

- Agree to practice two effective contraception measures during the entire study treatment period and through 90 days after the last dose of study drug, OR

- Agree to practice true abstinence or exclusively non-heterosexual activity when this is in line with the preferred and usual lifestyle of the subject. (Periodic abstinence (eg, calendar, ovulation, symptothermal, post-ovulation methods] and withdrawal are not acceptable methods of contraception.)

4. Patients must have a diagnosis of a chronic GVHD according to the NIH Consensus Criteria.¹⁰
5. Patients must have failed at least one prior line of systemic immune suppressive therapy for management of chronic GVHD.
6. Patients must meet the following clinical laboratory criteria:
 - Absolute neutrophil count (ANC) $\geq 1,000/\text{mm}^3$ and platelet count $\geq 75,000/\text{mm}^3$. Platelet transfusions are not allowed within 3 days before study enrollment.
 - Total bilirubin $\leq 1.5 \times$ the upper limit of the normal range (ULN).
 - Alanine aminotransferase (ALT) and aspartate aminotransferase (AST) $\leq 3 \times$ ULN.
 - Calculated creatinine clearance $\geq 30 \text{ mL/min}$ (see Section 11.2).

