7. STATISTICAL AND QUANTITATIVE ANALYSES

7.1 Statistical Methods

7.1.1 Determination of Sample Size and planned methods of analysis

The primary endpoint is overall treatment failure at 6 months from study enrollment. Treatment failure represents the composite including addition of new line of systemic immune suppressive therapy beyond Ixazomib (objective signal of failure to control GVHD with Ixazomib), non-relapse death, and primary malignancy relapse.²⁹ The historical benchmark for this outcome based on this analysis of 312 chronic GVHD patients is a 6 month treatment failure rate of 44%. With 50 patients, the standard error of the estimated failure rate will be approximately 7 percentage points.

With 50 subjects and a 1-sided alpha of 0.1, there will be 82% power to detect a 15 percentage point reduction in the 6 month treatment failure rate, relative to the reference rate of 44%, based on an exact binomial calculation using that option in nQuery. This reduction is deemed feasible based on the following: The major contribution to the observed treatment failure rate was 34% requiring additional immune suppressive therapy beyond second-line

therapy. Assuming effective therapy with ongoing Ixazomib over the treatment period could reduce this risk by 50% (i.e. to 17%) with little or no increased risk for relapse (3% in this published analysis) or non-relapse death (7% in this analysis), the overall improvement in the 6 month treatment failure rate could be 15%. Patients who are lost to follow up or otherwise not evaluable will not be replaced.

Although the overall 6 month failure rate in the historical benchmark study was 44%, this varied from 33% to 41% to 56% for patients that were classified as low, intermediate and high risk, respectively. Thus the relative proportions of patients in the different risk categories will need to be considered in order to interpret the possible benefit of Ixazomib therapy.

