Time-to-event endpoints will be evaluated using Kaplan-Meier and cumulative incidence methods; response endpoints will be evaluated as proportions; patient-reported outcomes will be summarized as frequencies, or with mean and SD, as appropriate. The only comparative analysis will involve the biologic endpoints, where responders at 3 and 6 months will be compared to nonresponders, based on baseline values and on changes from baseline. This will involve standard parametric or non-parametric methods, depending on the observed distribution of these endpoints.

In the analysis of secondary objectives, we will study the 3 and 6 month overall (complete + partial) response and complete response rates, other efficacy measures listed above, patient reported outcomes, and biologic outcome measures. We will study association between biologic outcome measures and clinical parameters (response, treatment failure, mortality).

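### Section 7.1.1 says the enrolled risk mix must be weighed when the failure rate is judged against 44%, but gives no method; an observed/expected comparison can be fixed in advance from the protocol's own rates

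*Combined protocol and SAP*

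**What the plan says.** The primary objective (Section 2.1) is "Determine the proportion of subjects with treatment failure by 6 months of Ixazomib treatment for chronic GVHD". Section 7.1.1 attaches a 1-sided alpha of 0.1 and 82% power to a 15-point reduction, "relative to the reference rate of 44%, based on an exact binomial calculation using that option in nQuery".

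The 44% comes from a published cohort of 312 patients given second-line treatment. Section 1.1.1 says of that cohort: "The cumulative incidence of 6 month treatment failure was 33% for low-risk, 41% for intermediate risk, and 56% for high risk". The groups are defined by 0, 1, or 2–3 of three factors: high-risk disease at transplantation, "lower gastrointestinal involvement as second-line treatment was added, and severe NIH global score as second-line treatment was added".

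Section 7.1.1 repeats the three rates and concludes that "the relative proportions of patients in the different risk categories will need to be considered in order to interpret the possible benefit" of ixazomib. The planned analyses that follow include no risk-adjusted one. Sections 5.1 and 5.2 set no quota on the three factors. The entry rule on prior treatment is "Patients must have failed at least one prior line of systemic immune suppressive therapy for management of chronic GVHD".

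**The concern.** In a single-arm trial the benchmark takes the place of a control group. If the enrolled patients are on average lower risk than the historical cohort, fewer than 44% would be expected to fail under ordinary second-line treatment, and a test against 44% calls benefit too readily. If they are higher risk, a real benefit is more easily missed. The same holds if the result is read only as an estimate, since one failure count means different things in different mixes.

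The protocol recognises this but leaves the method open. It could then be chosen after the failures have been counted, and the choice could change the conclusion.

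**Working it through.** **Inputs.** From Section 7.1.1: n = 50, 1-sided alpha 0.10, reference rate 0.44, target 0.29, stratum rates 0.33, 0.41 and 0.56. The enrolled mix is not in the documents; every mix below is an assumption.

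**1. The plan's own figure.** With X ~ Binomial(50, 0.44), P(X ≤ 17) = 0.099 and P(X ≤ 18) = 0.159, so the implied cut-off is 17. With X ~ Binomial(50, 0.29), P(X ≤ 17) = 0.826. The stated 82% reproduces.

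**2. Expected failures for a mix.** E = 0.33 nL + 0.41 nI + 0.56 nH.
- 20/20/10: 6.60 + 8.20 + 5.60 = 20.40, or 40.8%.
- 5/20/25: 1.65 + 8.20 + 14.00 = 23.85, or 47.7%.

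**3. Error rates.** If ixazomib does no better than the benchmark within each stratum, the failure count is the sum of three independent binomials, and its exact distribution is their convolution. The fixed rule is X ≤ 17. The standardised rule uses the largest cut-off c with exact lower-tail probability ≤ 0.10 for that mix. Power is shown for a uniform 15-point reduction and for a proportional one (each rate × 29/44).

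| Mix L/I/H | E (rate) | Fixed: alpha | Fixed: power uniform / proportional | Standardised: c | Standardised: alpha | Standardised: power uniform / proportional |
|---|---|---|---|---|---|---|
| 25/20/5 | 19.25 (38.5%) | 0.307 | 0.970 / 0.938 | 14 | 0.079 | 0.825 / 0.729 |
| 20/20/10 | 20.40 (40.8%) | 0.199 | 0.932 / 0.902 | 15 | 0.074 | 0.806 / 0.750 |
| 15/20/15 | 21.55 (43.1%) | 0.119 | 0.865 / 0.851 | 16 | 0.070 | 0.787 / 0.769 |
| 10/25/15 | 21.95 (43.9%) | 0.098 | 0.834 / 0.830 | 17 | 0.098 | 0.834 / 0.830 |
| 5/25/20 | 23.10 (46.2%) | 0.052 | 0.726 / 0.762 | 18 | 0.092 | 0.817 / 0.845 |
| 5/20/25 | 23.85 (47.7%) | 0.033 | 0.643 / 0.712 | 18 | 0.061 | 0.748 / 0.805 |

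**4. One result, two readings.** Seventeen failures of 50 give p = 0.099 against 44%. Standardised, observed/E is 17/19.25 = 0.88 (p = 0.31) in 25/20/5 and 17/23.85 = 0.71 (p = 0.033) in 5/20/25.

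**5. Which mixes are plausible?** A 44% average from rates of 33, 41 and 56% needs a high-risk share between (0.44 − 0.41)/(0.56 − 0.41) = 20% and (0.44 − 0.33)/(0.56 − 0.33) = 48%. The 25/20/5 mix has 10% high risk, at most half the benchmark's share, so it is an outer case.

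**6. Error in the benchmark itself.** A simple binomial standard error for 44% of 312 is √(0.44 × 0.56/312) = 2.8 points. One standard error either way moves the fixed rule's alpha to 0.19 (at 41.2%) or 0.046 (at 46.8%) with no change in mix. Standardising does not remove this. If all true stratum rates are 3 points lower, alpha in the six mixes, in table order, is:
- fixed rule: 0.476, 0.343, 0.228, 0.195, 0.117, 0.080;
- standardised rule: 0.166, 0.157, 0.148, 0.195, 0.185, 0.133.

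**7. Interval and test.** A convenient interval for observed/E is the exact binomial interval for the failure proportion divided by E/n. For 17 of 50 the exact 80% interval is 0.2506 to 0.4396. In 10/25/15 the test rejects (p = 0.098), but the upper limit is 0.4396/0.439 = 1.001. Over all 1,326 possible mixes of 50, the two imply different cut-offs in 80.

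**The case against.** The authors raise the issue themselves. In a 50-patient phase II trial the sentence can be read as an interpretive caution that a descriptive table by risk group would satisfy. The mixes are assumed. Standardising also has a price: its power is below 82% in four of the six mixes under either effect model, and it treats as known three stratum rates whose sample sizes the protocol does not give. These points stand, and they limit the weight of the finding. They do not supply the missing method. A table by risk group leaves the reader to decide afterwards how far the mix accounts for the result. The fixed rule's higher power in lower-risk mixes comes from its inflated alpha.

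A reader might go further and infer that the plan contradicts itself on whether any test is intended, because Section 7.1.1 also says "The only comparative analysis will involve the biologic endpoints". The documents do not support that. The sentence goes on to responders versus non-responders, so its natural meaning is comparison between groups of patients, not with a fixed historical rate. Nor does the wording of the primary objective exclude a test. The cut-off, though not printed, follows from the stated n, alpha, rate and exact method.

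A reader might also infer that this trial's false-positive rate is inflated, perhaps threefold. That follows only if the mix leans to lower risk, which nothing in the documents shows.

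**Conclusion.** The concern holds as a gap in specification. The sample-size calculation is right. The plan calls weighing the risk mix necessary for interpretation and does not say how to do it.

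The size is conditional. With the stratum rates taken as true, the fixed rule's alpha runs from 0.20 at 20/20/10, through 0.12 at 15/20/15, to 0.033 at 5/20/25, where power for a uniform 15-point reduction is 0.64. If the mix averages close to 44%, the two approaches agree. The direction of any departure is unknown.

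This is a change the sponsor should make because it is cheap and uses figures already in the protocol. It is not an error that invalidates the design.

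**What to change.** Add one paragraph to Section 7.1.1:

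1. **Classification.** Assign each patient at baseline to low, intermediate or high risk by the three factors in Section 1.1.1. The Study Calendar (11.1) already lists the NIH score; add disease risk at transplantation, lower gastrointestinal involvement and the derived group. Include a written scoring rule for enrolment, because the benchmark scored two factors when second-line treatment was added.
2. **Comparison.** Compute E = 0.33 nL + 0.41 nI + 0.56 nH. Report observed/E with the exact lower-tail p-value from the sum of the three binomials, 1-sided 0.10, beside the unadjusted comparison with 44%.
3. **Decision.** Name the standardised exact test in advance as the result used to interpret benefit. Label the binomial interval divided by E/n as descriptive, or obtain the interval by inverting the same test.
4. **Non-evaluable patients.** State how they count in both observed and E. They are not replaced, and enrolment is dated from consent (Section 4.2).
5. **Power.** State that 82% applies to a mix averaging 44%.

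A clause exempting the benchmark comparison from the sentence on comparative analyses would be optional clarification.

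The cost is that paragraph and a few baseline fields. Since "each participant must be approved by the coordinating center" before enrolment, the mix can be followed during accrual.

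The plan should state the downsides:
- The stratum rates are treated as known. If the true rates are 3 points lower, standardised alpha is 0.13–0.20 in the six mixes, and higher than the fixed rule's in the two higher-risk ones.
- Power ranges from 0.73 to 0.85 across the six mixes and both effect models.
- The cut-off (14 to 18 in these mixes) is final only when the mix is.
- Differences in line of therapy from the second-line cohort are not corrected.

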7.1.2 STUDY STOPPING RULES

While Ixazomib has demonstrated safety, it has not been previously studied in chronic GVHD therapy after allogeneic hematopoietic cell transplantation. Current evidence suggests that mortality after initiation of chronic GVHD therapy may be as high as 20% at 56 days in some high-risk patient groups (Blood and Marrow Transplant Clinical Trial Network Protocol 0801). In our current trial, we will implement a stopping rule based on a threshold rate of 10% treatment-related mortality occurring within 56 days (2 cycles) of starting treatment. If reasonable evidence exists that the rate on this trial exceeds this

threshold, then enrollment to the trial will be halted while data are reviewed. Reasonable evidence will be taken to mean that the lower bound of an exact 1-sided 80% confidence interval for the true non-relapse mortality rate exceeds 10%. The data will be evaluated at least every 10 patients, and will be triggered if 3 or more of 10, 4 or more of 20, 5 or more of 30, or 7 or more of 40 patients experience non-relapse mortality within the first 56 days.

Further details of the stopping rule include the following:

- (a) Treatment-related mortality is any death occurring while receiving study drug, or within 30 days after discontinuation of study drug, that is possibly, probably or definitely related to the drug
- (b) Relapse or progressive disease will factor into the attribution of cause, but will not automatically prevent a death from being classified as treatment-related
- (c) For purposes of this stopping rule, the count of patients (10, 20, etc) will reflect the order in which patients start treatment
- (d) If a DSMB review is required because the stopping rule is triggered, patients who are already enrolled and taking ixazomib may continue treatment, pending the outcome of that review. Any enrolled patient who has consented but not started study drug may not start ixazomib treatment, pending the outcome of that review.

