- **Musculoskeletal changes:** Avascular necrosis, fracture, arthritis, osteoporosis, decrease in range of motion associated with joint or fascial GVHD involvement
- **Sexual Function:** Erectile dysfunction, infertility, amenorrhea, vaginal stenosis, vaginal dryness or discomfort.
- **Events secondary to routine procedures performed for chronic GVHD therapies:** Extracorporeal photopheresis, PUVA therapy.

Non-serious adverse events collected in the database will be compiled by the coordinating center and reported to the DSMB approximately every 6 months.

All **serious adverse events** must be reported in the database within 24 hours of becoming aware of the event. Significant and relevant follow-up information should also be reported as soon as possible.

- **Exception:**
 - Hospitalization for elective treatment of a pre-existing condition that did not worsen from baseline is not considered an SAE.

The database will notify the coordinating center and sponsor-investigator when a serious adverse event has been entered. The sponsor-investigator will then determine whether the event meets the criteria for expedited reporting (see below) and will work with the coordinating center to prepare the IND Safety Report.

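### The mortality rule does not require a halt when a death makes a listed limit certain; halting then leaves the stopping probability unchanged and saves about 2.4 patients at a true 20% rate

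*Combined protocol and SAP*

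**What the plan says.** Section 7.1.2 bases the rule on a "threshold rate of 10% treatment-related mortality occurring within 56 days (2 cycles) of starting treatment". Enrollment is halted for review when there is reasonable evidence of a higher rate, defined as the "lower bound of an exact 1-sided 80% confidence interval for the true non-relapse mortality rate exceeds 10" per cent. The operating version reads: "The data will be evaluated at least every 10 patients, and will be triggered if 3 or more of 10". Three later limits are listed in the same sentence: 4 deaths in 20 starters, 5 in 30 and 7 in 40. Item (c) adds that "the count of patients (10, 20, etc) will reflect the order in which patients start treatment". Under item (d), while a triggered review is pending, consented patients who have not begun study drug may not start.

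The section also sends all deaths through 6 months to the DSMB for discussion as needed, and gives a table of stopping probability and average N by true event rate. Section 4.2 caps the trial ("A total of 50 patients will be enrolled") and has the coordinating center approve each participant. Section 8.2 says that serious adverse events "must be reported in the database within 24 hours of becoming aware of the event", and that the database then notifies the coordinating center and the sponsor-investigator.

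**The concern.** The limits do not fall from one look to the next and a death count cannot go down. When the limiting death occurs part-way through a block, the outcome of that block's look is settled. The text nevertheless requires an evaluation only once per ten patients, so new patients can start treatment although a halt is bound to follow.

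For example, take 2 deaths among the first 10 starters and 2 more among patients 11 to 13. That is 4 deaths, so the limit of 4 in 20 will be met whatever happens to patients 14 to 20. Up to seven more patients could start before the next required look. At stake are patients started after the protocol's own ground for halting is certain to be met. The point is the same whether the counted event is treatment-related or non-relapse mortality; the section uses both terms.

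**Working it through.** **Inputs.** Limits r of 3/10, 4/20, 5/30 and 7/40, the 10% threshold, the one-sided 80% criterion and the tabulated true rates (all Section 7.1.2); maximum N of 50 (Section 4.2).

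**1. The limits follow from the criterion.** The 80% lower bound exceeds 10% exactly when P(X ≥ r | n, 0.10) < 0.20.

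| n | r | P(X ≥ r) | P(X ≥ r − 1) |
|---|---|---|---|
| 10 | 3 | 0.070 | 0.264 |
| 20 | 4 | 0.133 | 0.323 |
| 30 | 5 | 0.175 | 0.353 |
| 40 | 7 | 0.100 | 0.206 |

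Each r is the smallest count that qualifies.

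**2. The plan's average N.** Let D(n,k) be the probability of k deaths among the first n starters without a stop. Then D(n,k) = (1 − p)·D(n−1,k) + p·D(n−1,k−1). For block looks, remove k ≥ r at n = 10, 20, 30 and 40 only. Average N = Σ n·P(stop at n) + 50·P(no stop).

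**3. Halting on the limiting death.** Use the same recursion, but at every n remove k ≥ r for the next listed look. In both versions the trial stops if and only if, for some listed n, at least r of the first n starters die. The probability of stopping is therefore identical, and only the timing moves.

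| True rate | Average N, plan's table | Block looks | Halt on limiting death | Saving | P(stop), both |
|---|---|---|---|---|---|
| 5% | 49 | 49.1 | 49.0 | 0.07 | 3.0% |
| 10% | 43 | 43.2 | 42.6 | 0.6 | 23.5% |
| 15% | 34 | 33.5 | 32.0 | 1.5 | 56.3% |
| 20% | 25 | 24.7 | 22.3 | 2.4 | 82.0% |
| 25% | 19 | 18.8 | 15.7 | 3.0 | 94.5% |

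The block column reproduces the plan's average N. At 20%, block looks give 0.820 × 19.16 + 0.180 × 50 = 24.7, and halting on the limiting death gives 0.820 × 16.19 + 0.180 × 50 = 22.3. Among trials that stop, the saving is 19.16 − 16.19 = 2.97 patients.

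**4. The stopping probabilities.** With the four printed limits, the values at 20% and 25% (82.0% and 94.5%) fall short of the table's 87% and 97%. Adding an unprinted look at 50 with a limit of 8 gives 25.6%, 62.3%, 87.6% and 97.3% at 10% to 25%, close to the table's 25%, 62%, 87% and 97%. That look cannot change block average N, since N is 50 either way. Halting on the limiting death again leaves the probability unchanged and saves 2.6 patients at 20%.

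**5. The evidence criterion in the example.** For 4 deaths in 13, P(X ≥ 4 | 13, 0.10) = 0.034, and the exact 80% lower bound is 18.2%. Counting patients still inside their 56 days as survivors is conservative, because the count can only rise.

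**6. With a 56-day window.** Assumptions: 20% rate, deaths uniform over 56 days, random arrivals, 1 to 4 starts per month. The table gives patients saved by halting on the limiting death, from simulation.

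| Starts per month (assumed) | Block look acts once block is full and limit met | Block look waits 56 days after the last start in the block |
|---|---|---|
| 1 | 1.8 | 3.2 |
| 2 | 1.4 | 3.9 |
| 4 | 0.7 | 5.1 |

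Repeat simulations move these by up to about 0.3 patients, so the overall range is about 0.6 to 5.

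**The case against.** **The text is less tied to blocks than it looks.** The general sentence halts enrollment whenever reasonable evidence exists, and the evaluation interval is a minimum frequency. Both are true, and a sponsor could act early. But a permission is not a requirement, and the table describes block looks. If the confidence criterion were applied afresh at every patient, the stopping probability at a true 10% would be 45%, not the tabulated 25%, so that cannot be the rule that was evaluated.

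**Other controls exist.** The coordinating center can slow enrollment, and the DSMB hears of every death through 6 months. These make an early hold practicable; neither orders one.

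**The benefit depends on the scenario.** This stands. The protocol's 20% figure describes some high-risk groups and is not an estimate for this trial. Section 5.2 excludes Karnofsky status below 70% and life expectancy under 6 months, and the benchmark non-relapse death rate in Section 7.1.1 is 7%. At true rates of 10% or less the average saving is 0.6 patients or fewer.

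**A reader might infer a saving of 4 to 5 patients at a 20% rate.** The documents do not support that as a general figure. It needs both an accrual rate, which they do not give, and a full 56-day wait after each block, which the rule does not state.

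**A reported death is not yet an attributed one.** This also stands: items (a) and (b) of Section 7.1.2 require attribution, so 24-hour entry alone does not settle whether a death counts. The fix has to allow for it.

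**Conclusion.** The gap is real but modest. Section 7.1.2 permits an earlier look and does not require a halt when a listed limit has become certain. Closing the gap does not change the false-alarm probability. In the table's own framework it saves 2.4 patients on average at a true 20% rate and 3.0 at 25%, and almost none when early mortality is low.

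The exact figures rest on the four printed limits and on outcomes known before the next start. The wider range of about 0.6 to 5 patients at 20% rests on assumed accrual of 1 to 4 per month, uniform death times, and how long the block look waits. The unprinted look at 50 does not alter the conclusion. It would be wrong to read the point as saying that the plan forbids early action or that this regimen carries 20% early mortality.

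**What to change.** Add to Section 7.1.2 that the count is checked at each reported death classified as qualifying under the section's definition, and name the role that classifies it. If a death would meet a limit and attribution is pending, new enrollment and treatment starts are provisionally held. They are halted for review once the 3rd such death among the first 10 starters, the 4th among the first 20, the 5th among the first 30 or the 7th among the first 40 is reached, without waiting for the block to fill.

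Keep the listed limits. Do not replace them with the confidence criterion applied at every patient, which is a different rule with a much higher stopping probability.

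Restate the average N column: 49.0, 42.6, 32.0, 22.3 and 15.7 with the four printed limits. Either print the limit at 50 or correct the probability column; if a limit of 8 at 50 is printed, average N at 20% becomes 22.1.

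The cost is a few sentences and a revised table. Death reporting and enrollment approval are already in place, and no extra data are needed. The downside is an occasional short hold for a death later judged not to qualify.
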